## **7. PLANNED ANALYSIS**

The format of the listings and tables will follow the BI guideline "Standards for Reporting of clinical trials and project summaries" ([6](#)).

The individual values of all subjects will be listed. Listings will be sorted by subject number, visit and planned time point (if visit/ planned time point is applicable in the respective listing). The listings will be contained in Appendix 16.2 (SDL) of the CTR.

The following standard descriptive statistical parameters will be displayed in summary tables of continuous variables:

N	number of non-missing observations
Mean	arithmetic mean
SD	standard deviation
Min	minimum
Median	median
Max	maximum

For plasma concentrations as well as for all PK parameters the following descriptive statistics will additionally be calculated:

CV	arithmetic coefficient of variation
gMean	geometric mean
gCV	geometric coefficient of variation

For PK parameters the following descriptive statistics will additionally be calculated:

P10	10 th percentile
Q1	1 st quartile
Q3	3 rd quartile
P90	90 th percentile

The data format for descriptive statistics of plasma concentrations will be identical with the data format of the respective concentrations. The descriptive statistics of PK parameters will be calculated using the individual values with the number of decimal places as provided by the evaluation program. Then the individual values as well as the descriptive statistics will be reported with three significant digits in the CTR.

Tabulations of frequencies for categorical data will include all possible categories and will display the number of observations in a category as well as the percentage (%) relative to the respective treatment group. Percentages will be rounded to one decimal place. The category missing will be displayed if and only if there actually are missing values. Percentages will be based on all subjects in the respective subject set whether they have non-missing values or not.

## 7.1 DEMOGRAPHIC AND OTHER BASELINE CHARACTERISTICS

Only descriptive statistics are planned for this section of the CTR. These will be based on the TS.

## 7.2 CONCOMITANT DISEASES AND MEDICATION

Concomitant diseases will be coded according to the most recent version of MedDRA. Concomitant medication will be coded according to the most recent version of the World Health Organisation – Drug Dictionary. Concomitant non-drug therapies will be coded according to the most recent version of MedDRA.

Only descriptive statistics are planned for this section of the CTR.

**CTP:** *Previous and concomitant therapies will be presented without consideration of time intervals and treatment periods.*

A medication will be considered concomitant, if it

- is ongoing at the time of study drug administration, or
- starts within the on-treatment phase of the respective treatment (see [Section 6.1](#) for a definition of treatments and analysis phases).

The relevance of the concomitant therapies to the evaluation of PK will be decided no later than at the RPM.

## 7.3 TREATMENT COMPLIANCE

Treatment compliance will not be analyzed as a specific endpoint. Any deviations from complete intake will be addressed in the Report Planning Meeting (cf. [Section 6.2](#)) and described in the CTR.

## 7.4 PRIMARY ENDPOINTS

### 7.4.1 Primary analysis of the primary endpoints

Descriptive statistics are planned for this section of the CTR. Furthermore, relative bioavailability will be evaluated using the following model based approach:

**CTP:**

#### Primary analyses

*The statistical model used for the analysis of the primary endpoints (refer to Section 2.1.2) will be an analysis of variance (ANOVA) model on the logarithmic scale. That is, the PK endpoints will be log-transformed (natural logarithm) prior to fitting the ANOVA model. This model will include effects accounting for the following sources of variation: subjects and treatment. The effect 'subjects' will be considered as random, whereas the effect 'treatment' will be considered as fixed. The model is described by the following equation:*

$y_{km} = \mu + s_m + \tau_k + e_{km}$ , where

$y_{km}$  = logarithm of response measured on subject  $m$  receiving treatment  $k$ ,  
 $\mu$  = the overall mean,  
 $s_m$  = the effect associated with the  $m^{\text{th}}$  subject,  $m = 1, 2, \dots, 15$   
 $\tau_k$  = the  $k^{\text{th}}$  treatment effect,  $k = 1, 2$ ,  
 $e_{km}$  = the random error associated with the  $m^{\text{th}}$  subject who received treatment  $k$ . where  $s_m \sim N(0, \sigma_R^2)$  i.i.d.,  $e_{km} \sim N(0, \sigma_W^2)$  i.i.d. and  $s_m, e_{km}$  are independent random variables.

Point estimates for the ratios of the geometric means (test/reference) for the primary endpoints (see Section 2.1) and their two-sided 90% confidence intervals (CIs) will be provided.

For each endpoint, the difference between the expected means for  $\log(T)$ - $\log(R)$  will be estimated by the difference in the corresponding adjusted means (Least Squares Means). Additionally their two-sided 90% confidence intervals will be calculated based on the residual error from the ANOVA and quantiles from the  $t$ -distribution. These quantities will then be back-transformed to the original scale to provide the point estimate and 90% CIs for each endpoint.

#### Further exploratory analyses

The same statistical model as stated above will be repeated for the primary endpoints but with all sources of variation ('subjects', 'treatment') considered as fixed effects.

In addition to the model based approach all parameters will be calculated and analyzed descriptively.

Analyses of primary endpoints will be based on the PKS.

#### Exclusion of PK parameters

The ADS ADPP contains column variables APEXC and APEXCO indicating inclusion/exclusion (APEXC) of a PK parameter and an analysis flag comment (APEXCO). All analyses based on the PKS are based on PK parameter values which are not flagged for exclusion, i.e. with APEXC equal to "Included".

**CTP:** Plasma concentration data and parameters of a subject which is flagged for exclusion will be reported with its individual values but will not be included in the statistical analyses.

#### Exclusion of plasma concentrations

The ADS ADPC (PK concentrations per time-point or per time-interval) contains column variables ACEXC or ACEXCO indicating inclusion/exclusion (ACEXC) of a concentration and an analysis flag comment (ACEXCO). Exclusion of a concentration depends on the analysis flag comment ACEXCO. For example, if ACEXCO is set to "ALL CALC", the value will be excluded for all types of analyses based on concentrations. If ACEXCO is set to "DESC STATS" the value will be excluded from descriptive evaluations per planned time point/time interval. If ACEXCO contains the addition "TIME VIOLATION" or "TIME DEVIATION", the value can be used for further analyses based on actual times. If ACEXCO is set to "HALF LIFE", the value will be excluded from half-life calculation only; the value is

included for all other analyses. Excluded concentration itself will be listed in the CTR associated with an appropriate flag.

Further details are given in “Noncompartmental Pharmacokinetic/ Pharmacodynamic Analyses of Clinical Studies” [\(4\)](#) and “Description of Analytical Transfer Files and PK/PD Data Files” [\(5\)](#).

## 7.5 SECONDARY ENDPOINTS

### 7.5.1 Key secondary endpoints

This section is not applicable as no key secondary endpoint has been specified in the protocol.

[figure not shown]
### 7.5.2 Secondary endpoints

[figure not shown]
The analysis of secondary PK endpoints will be based on the PKS.

#### 7.5.2.1 Secondary endpoint analysis

**CTP:** *The secondary endpoints (refer to Section 2.1.3) will be calculated according to the relevant BI internal procedures and will be assessed statistically using the same methods as described for the primary endpoints.*

Exclusion of PK parameters and exclusion of plasma concentrations are handled as described in [Section 7.4.1](#).

## 7.7 EXTENT OF EXPOSURE

Descriptive statistics are planned for this section of the report.

## 7.8 SAFETY ANALYSIS

All safety analyses will be performed on the TS.

### 7.8.1 Adverse Events

AEs will be coded with the most recent version of MedDRA.

The analyses of AEs will be descriptive in nature. All analyses of AEs will be based on the number of subjects with AEs and not on the number of AEs.

For further details on summarization of AE data, please refer to “Analysis and Presentation of Adverse Event Data from Clinical Trials” [\(7\)](#) and “Handling of missing and incomplete AE dates” [\(3\)](#).

The analysis of AEs will be based on the concept of treatment emergent AEs. That means that all AEs will be assigned to screening, on-treatment or follow-up phases as defined in [Section 6.1](#). AEs will be analysed based on actual treatments, as defined in [Table 6.1: 1](#).

An overall summary of AEs will be presented. This overall summary will comprise summary statistics for the class of AESIs.

**CTP:** *Hepatic injury is considered an AESI in this trial. A hepatic injury is defined by the following alterations of hepatic laboratory parameters:*

- *An elevation of AST (aspartate transaminase) and/or ALT (alanine transaminase)  $\geq 3$  fold ULN combined with an elevation of total bilirubin  $\geq 2$  fold ULN measured in the same blood sample, or*
- *Aminotransferase (ALT, and/or AST) elevations  $\geq 10$  fold ULN*

The investigator had to classify on the eCRF whether an observed AE was an AESI or not.

According to ICH E3 (8), in addition to Deaths and Serious Adverse Events, ‘other significant’ AEs need to be listed in the clinical trial report. These will be any non-serious adverse event that led to an action taken with study drug (e.g. discontinuation or dose reduced or interrupted).

The frequency of subjects with AEs will be summarised by treatment, primary SOC and preferred term. AEs which were considered by the investigator to be drug related will be summarised separately. Separate tables will also be provided for subjects with SAEs and subjects with AESIs. AEs will also be summarized by maximum intensity.

The SOC and preferred terms within SOC will be sorted by descending frequency.

For disclosure of AE data on ClinicalTrials.gov, the frequency of subjects with non-serious AEs occurring with an incidence of greater than 5 % (in preferred terms) will be summarised by primary SOC and preferred term. The frequency of subjects with SAEs will also be summarised.

For disclosure of AE data in the EudraCT register, the frequency of AEs, the frequency of non-serious AEs with an incidence of greater than 5 % (in preferred terms) and the frequency of SAEs will be summarized.

For support of lay summaries, the frequency of subjects with drug-related SAEs will be summarized by treatment, primary SOC and preferred term.

### 7.8.2 Laboratory data

The analyses of laboratory data will be descriptive in nature and will be based on BI standards "Display and Analysis of Laboratory Data" (9).

Analyses will be based on normalised values, which means transforming to a standard unit and a standard reference range. The original values will be analysed if the transformation into standard unit is not possible for a parameter.

Descriptive statistics of laboratory values over time and for the difference from baseline (see Section 6.7) will be provided. Frequency tables of changes between baseline and last value on treatment with respect to the reference range will be presented.

Unscheduled measurements of laboratory data will be assumed to be repeat measurements of the most recent scheduled measurement (e.g. for follow-up or confirmation of a particular

value). Therefore, unscheduled measurements will be assigned to the planned time point of the previous scheduled measurement. Descriptive statistics will be calculated by planned time point based on the worst value of the subject at that planned time point (or assigned to that planned time point).

Clinically significant abnormal laboratory values are only those identified either in the Investigator's comments or at the Report Planning Meeting at the latest. It is the Investigator's responsibility to decide whether a lab value is clinically significant abnormal or not.

Laboratory data will be compared to their reference ranges. Values outside the reference range as well as possibly clinically significant values will be highlighted in the listings. Possibly clinically significant laboratory values will be listed in Section 15.4.1.

Clinically relevant findings in laboratory data will be reported as baseline conditions (prior to first administration of study treatment) or as AEs (after first administration of study treatment) if judged clinically relevant by the investigator, and will be analyzed as such.

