6.2.3 Follow-up period and trial completion

For AE assessment, laboratory tests, recording of ECG and vital signs, and physical examination during the follow-up period, see Section 5.2.

Subjects who discontinue treatment before the end of the planned treatment period should undergo the EoTrial Visit.

All abnormal values (including laboratory parameters) that are assessed as clinically relevant by the investigator will be monitored using the appropriate tests until a return to a medically acceptable level is achieved. (S)AEs persisting after a subject's EoTrial Visit must be followed until they have resolved, have been sufficiently characterised, or no further information can be obtained.

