## **6. GENERAL ANALYSIS DEFINITIONS**

### **6.1 TREATMENTS**

For basic study information on the treatment to be administered, and selection of dose, cf. Section 4 of the CTP.

Subjects will receive the following two treatments in a fixed sequence (reference treatment always followed by test treatment).

In Period Reference R, all subjects will receive 1 tablet containing

- 10 mg BI 425809 (Reference Treatment R) as a single dose

Afterwards, in Period Test T, all subjects will receive

- 2 capsules, each containing 200 mg Fluconazole, once daily for 13 days (Day -4 to Day 9) and 1 tablet containing 10 mg BI 425809 as a single dose on Day 1 (Test Treatment T).

For statistical analysis of AEs, the following analysis phases are defined for each subject.

Table 6.1: 1 Analysis phases for statistical analysis of AEs, and actual treatment for analysis of laboratory data and vital signs

Study analysis phase	Label	Start	End
Screening 	Screening	Date of informed consent	Date/time of first administration of BI 425809
On treatment	BI 425809	Date/time of first administration of BI 425809	Date/time of first administration of BI 425809 + REP (11 days) or 12:00 a.m. on day after last contact date (whichever occurs first)
Follow-up	F/U BI 425809	Date/time of first administration of BI 425809 + REP (11 days)	Date/time of first administration of Fluconazole or 12:00 a.m. on day after last contact date (whichever occurs first)
On treatment	Fluconazole	Date/time of first administration of Fluconazole	Date/time of second administration of BI 425809 or 12:00 a.m. on day after last contact date (whichever occurs first)
On treatment	BI + Fluconazole	Date/time of second administration of BI 425809	Date/time of second administration of BI 425809 + REP (14 days) or 12:00 a.m. on day after last contact date (whichever occurs first)
Follow-up	F/U BI + Fluconazole	Date/time of second administration of BI 425809 + REP (14 days)	12:00 a.m. on day after last contact date

 See [Section 6.7](#) for definition of baseline, which will be used in the statistical analyses of safety laboratory data and vital signs.

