The on-treatment phase for 'BI + Fluconazole' includes both the REP for BI 425809 (14 days) and Fluconazole (6 days). Since the second administration of BI 425809 is scheduled at 9:00 am on Visit 3, Day 1, while the last administration of Fluconazole is scheduled at 8:00 am on the Visit 3, Day 9 (see CTP, Flow chart). Therefore, Date/time of the second administration of BI 425809 + REP (14 days) is one hour after Date/time of the last administration of Fluconazole + REP (6 days).

AE summary tables will present results for the on-treatment phases only. All AEs will be listed.

In AE tables in CTR Section 15.3 (but not in Appendix 16.1.13.1.8.1 and Appendix 16.1.13.1.8.2 AE tables), the following totals will be provided in addition:

- **"Total BI"**, defined as the total over all on-treatment phases involving BI 425809
- **"Total Fluconazole"**, defined as the total over all on-treatment phases involving Fluconazole
- **"Total on-trt"**, defined as the total over all on-treatment phases

Safety laboratory data, vital signs and PK parameters will be analyzed based on treatment periods (BI 425809 and BI+Fluconazole) with clear differentiation between baseline (cf. [Section 6.7](#)) and post-baseline measurements. Measurements will be considered on-treatment, if they were taken within the on-treatment phases of BI 425809 or BI+Fluconazole as defined in [Table 6.1: 1](#). More details on the technical implementation of these analyses are provided in the ADS Plan of this TSAP.

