## **6.7 BASELINE, TIME WINDOWS AND CALCULATED VISITS**

For both periods, the last available value determined prior to administration of BI 425809 will be defined as baseline.

Time windows are defined in Section 6.1 of the CTP. Adherence to time windows will be checked at the Report Planning Meeting.

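### Laboratory shift tables use only the last on-treatment value, so a transient liver-enzyme rise that is back in range by then counts as normal-to-normal

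*SAP*

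**What the plan says.** SAP 7.8.2 (Laboratory data) specifies the shift tables in one sentence: "Frequency tables of changes between baseline and last value on treatment with respect to the reference range will be presented". It specifies no shift table against any other on-treatment value.

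Three other rules decide which value that is:

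- **On-treatment window (SAP 6.1).** "Measurements will be considered on-treatment, if they were taken within the on-treatment phases of BI 425809 or BI+Fluconazole". Table 6.1: 1 ends the Treatment T phase 14 days after the second BI 425809 dose and the Treatment R phase 11 days after the first, or at last contact if earlier.
- **Baseline (SAP 6.7).** "For both periods, the last available value determined prior to administration of BI 425809 will be defined as baseline". In Treatment T this falls after four fluconazole doses (Days -4 to -1).
- **Unscheduled samples (SAP 7.8.2).** They are treated as repeats: "unscheduled measurements will be assigned to the planned time point of the previous scheduled measurement". The next rule is "Descriptive statistics will be calculated by planned time point based on the worst value of the subject at that planned time point". It is stated for descriptive statistics; whether it also governs the shift tables is not said.

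The protocol Flow Chart and Table 5.2.3: 1 give the sampling. Post-baseline panels in Treatment T are Day 2 (set B) and Days 4, 6 and 8 (set C). In Treatment R they are Day 2 (set B) and Day 10 (set C). Set C contains AST, ALT, alkaline phosphatase and GGT, but not bilirubin.

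**The concern.** In SAP 7.8.2 the shift table is the only display that counts subjects moving across the reference range. If it looks only at the last value, a rise that comes and goes within the on-treatment phase leaves no trace in that count.

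This matters most for the liver enzymes. Protocol 1.4.3.2 lists increases in ALT, AST and alkaline phosphatase as common with fluconazole, and names regular liver monitoring during dosing as a risk mitigation. Treatment T has four post-baseline enzyme panels, and on scheduled data the table uses one of them. A reader of the report could take a row of normal-to-normal counts as showing that enzymes stayed in range throughout, which the table cannot show.

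**Working it through.** **1. On-treatment window (hours after BI 425809).** In T it ends at 14 × 24 = 336 h, which is Day 15, 09:00. The last fluconazole dose is at 191 h, and adding its 6-day residual effect period gives 191 + 144 = 335 h. The difference is 1 h, as SAP 6.1 states. In R the window ends at 11 × 24 = 264 h, which is Day 12, 09:00.

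**2. Scheduled liver-enzyme panels inside the window.**

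- T: Days 2, 4, 6 and 8 (24, 71, 119 and 167 h). The last is 336 − 167 = 169 h before the window closes.
- R: Days 2 and 10 (24 and 215 h). The last is 264 − 215 = 49 h before the window closes.
- The scheduled end-of-trial panel is on Day 16 to 30. Its earliest time, Day 16 at 00:00, is 15 × 24 − 9 = 351 h, after the T window has closed.
- Bilirubin has one scheduled post-baseline on-treatment value per period, on Day 2.

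**3. Patterns on scheduled data, normal baseline.** In T there are 2⁴ = 16 normal/abnormal patterns, of which 16 − 1 = 15 have at least one abnormal value. Those ending normal on Day 8 number 2³ − 1 = 7. In R the figures are 2² − 1 = 3 and 2¹ − 1 = 1. A worst-value table misses 0 of 15 and 0 of 3. These are counts of possibilities; the documents give no rates from which to derive expected numbers.

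**4. Assumed ALT courses in T under each reading of the rule.** Baseline is normal. N→N means tabulated as normal-to-normal, N→H as normal-to-high.

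| Course | Last in time | Last planned time point, worst value within it | Last scheduled | Worst on treatment |
|---|---|---|---|---|
| A: high Day 4, normal Day 8, no later sample | N→N | N→N | N→N | N→H |
| B: high Day 8, unscheduled normal Day 12 | N→N | N→H | N→H | N→H |
| C: normal Day 8, unscheduled high Day 10 and normal Day 14 | N→N | N→H | N→N | N→H |
| D: high Days 6 and 8, unscheduled normal Day 14 | N→N | N→H | N→H | N→H |

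Course A loses the rise under every reading of the last value. It was run at 2 × ULN on Day 4, below the 3-fold criterion for stopping treatment in Protocol 3.3.4.1, and assumes that the next-day control does not lead to discontinuation. Courses B to D turn on how unscheduled samples are handled, which SAP 7.8.2 leaves open for the shift tables.

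**5. Weight of one subject.** 1/15 = 6.7 percentage points of the planned sample.

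**The case against.** The best defence is that individual rises remain visible elsewhere. SAP 7.8.2 provides statistics over time built on worst values, highlights out-of-range results in the listings, lists possibly clinically significant values in CTR Section 15.4.1, and reports clinically relevant findings as adverse events. SAP 7 includes the maximum in every continuous summary. With 15 subjects, a medical reader will find the rise. This stands and limits the point to one table. It does not remove it: none of these displays gives a count of subjects by treatment who left the reference range, and adverse event reporting depends on the investigator's judgement.

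A second defence is that worst-value tables favour the arm with fewer draws. T has four scheduled enzyme panels and R has two, so T has more chances to show an abnormal value. This also stands, and the added table must carry a warning.

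A third is that the sponsor's internal laboratory standard, cited in SAP 7.8.2, may define the last value. It may; it is not available here.

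A reader might go further and infer that the follow-up rule in Protocol 6.2.3, under which clinically relevant abnormal values "will be monitored using the appropriate tests until a return to a medically acceptable level is achieved", systematically erases the important rises. The documents do not support that:

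- After Day 8 in T, recovery inside the window can be seen only in unscheduled samples or an early-discontinuation examination, and the planned-time-point rule may keep the abnormal value.
- The scheduled Day 16 to 30 panel is outside the T window and cannot overwrite anything.
- A medically acceptable level need not be within the reference range.
- A subject already high at the T baseline could not be tabulated as normal-to-normal.

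Nor do the two laboratory rules contradict each other. One chooses among repeats within a planned time point; the other chooses which value is compared with baseline.

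**Conclusion.** The point holds in a limited form. The only laboratory shift table planned in SAP 7.8.2 counts a liver-enzyme rise as normal-to-normal when the period baseline was normal and the last on-treatment sample is back in range. On scheduled T data it ignores three of four post-baseline panels, and 7 of the 15 patterns containing an abnormality are hidden.

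The certain part is a rise on Days 2 to 6 that has resolved by the Day 8 panel and stays in range in any later on-treatment sample. For rises that lead to stopping treatment, or that appear on or after Day 8, the classification depends on the unstated handling of unscheduled samples and could go either way. For bilirubin, masking needs an unscheduled or early-discontinuation sample.

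No number of affected subjects can be predicted from the documents. The primary and secondary endpoints are untouched, no data are lost, and the consequence is confined to one descriptive safety table. The change is a cheap improvement that should be made.

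**What to change.** In SAP 7.8.2:

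1. Add a shift table of baseline against the worst (highest) on-treatment value for AST, ALT, alkaline phosphatase and GGT, and for bilirubin where repeats exist. Include unscheduled values taken inside the on-treatment phases of Table 6.1: 1.
2. Keep the baseline-to-last table, which shows the state at the last on-treatment sample.
3. State which value counts as the last on treatment when repeats exist: the last in time, the last scheduled, or the value retained for the last planned time point.
4. Footnote the new table: T has four scheduled post-baseline liver-enzyme panels and R has two, so worst-value frequencies are not directly comparable between treatments.

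The cost is two or three sentences and one additional table, with no new data collection. The downside is the unequal number of draws, which the footnote discloses but does not remove.

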### **7.8.3 Vital signs**

The analyses of vital signs (blood pressure and pulse rate) will be descriptive in nature. Descriptive statistics of vital signs over time and for the difference from baseline (see [Section 6.7](#)) will be provided.

Unscheduled measurements of vital signs will be assigned to planned time points in the same way as described above for laboratory data. However, for vital signs, descriptive statistics will be calculated by planned time point based on the last value of the subject at that planned time point (or assigned to that planned time point). If the time of measurement is missing for a scheduled post-baseline measurement, the scheduled measurement will be used in calculation of descriptive statistics (as time difference between scheduled and unscheduled cannot be assessed).

If the time of measurement is missing for an unscheduled measurement, this measurement will be listed but will be ignored for the calculation of descriptive statistics.

Clinically relevant findings in vital signs data will be reported as baseline conditions (prior to first administration of study treatment) or as AEs (after first administration of study treatment) if judged clinically relevant by the investigator, and will be analyzed as such.

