### **7.8.4 ECG**

Abnormal findings in ECG will be reported as baseline conditions (at screening) or as AEs (during the trial) if judged clinically relevant by the investigator, and will be analyzed as such. No separate listing or analysis of ECG data will be prepared.

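### SAP 7.8.2 and 7.8.3 carry unscheduled laboratory values and timed vital signs back to the previous planned time point without stopping at a dose, so a by-time-point summary can show them in the wrong place

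*SAP*

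**What the plan says.** SAP 7.8.2 starts from a premise: "Unscheduled measurements of laboratory data will be assumed to be repeat measurements of the most recent scheduled measurement". It draws the consequence: "Therefore, unscheduled measurements will be assigned to the planned time point of the previous scheduled measurement". The summary then takes the least favourable value in each slot: "Descriptive statistics will be calculated by planned time point based on the worst value of the subject at that planned time point".

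SAP 7.8.3 follows suit: "Unscheduled measurements of vital signs will be assigned to planned time points in the same way as described above for laboratory data". The difference is that the last value in the slot is used, not the worst. An unscheduled vital sign without a recorded time is outside the rule: "this measurement will be listed but will be ignored for the calculation of descriptive statistics". ECGs are outside it too, under SAP 7.8.4: "No separate listing or analysis of ECG data will be prepared".

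Three other places bear on the point:

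- SAP 6.1 analyses laboratory data and vital signs by treatment period, promises a clear separation of baseline from later values, and sets on-treatment status by the time of measurement: "Measurements will be considered on-treatment, if they were taken within the on-treatment phases of BI 425809 or BI+Fluconazole".
- SAP 6.7 fixes baseline in each period: "the last available value determined prior to administration of BI 425809 will be defined as baseline".
- Protocol 7.3.4 assigns a measurement to the treatment in force at its planned time. SAP 4 says that the SAP agrees with the protocol's methods.

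No passage says which rule prevails when a carried-back value crosses a dose.

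**The concern.** The repeat premise suits a haemolysed sample or a confirmation of an odd result. It does not suit a test prompted by a new symptom, and the protocol foresees such tests. Section 5.2.5.1.4 asks for liver parameters in an unscheduled blood test if needed when symptoms of hepatic injury appear. Section 5.2.3 allows retests at the investigator's discretion. Section 6.2.3 requires relevant abnormal values to be followed until acceptable.

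If a dose lies between the last scheduled measurement and the ad hoc one, the carry-back places an after-dose value in a before-dose row. If the first fluconazole dose lies between, a fluconazole value goes into a row of the BI 425809-alone period. A laboratory value carried back in this way displaces the true one in the summary whenever it is worse. A vital sign displaces it whenever it is later, which it always is here.

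What is at stake is the readability of the descriptive safety tables. Hepatic injury is the adverse event of special interest, and raised liver enzymes are a listed fluconazole reaction (protocol 1.4.3.2), so a liver value shown in the wrong row is the case that matters most.

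**Working it through.** **Inputs.** From the protocol Flow Chart, in hours relative to BI 425809 in the same period:

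- Scheduled laboratory samples: R at -2, 24 and 215; T at -25, -2, 24, 71, 119 and 167.
- Scheduled vital signs, as extracted: R at -2 only; T at -2, 3 and 24.
- First fluconazole dose: T at -97.

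From protocol 3.1: at least 16 days between BI 425809 doses, so 16 × 24 = 384 h. From SAP Table 6.1: 1: the BI 425809-alone phase ends 11 days after the first dose, so 11 × 24 = 264 h.

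**Step 1, the plan's own timeline figure.** SAP 6.1 says that the second BI 425809 dose plus 14 days falls one hour after the last fluconazole dose plus 6 days. Day 1 09:00 + 14 d = Day 15 09:00. Day 9 08:00 + 6 d = Day 15 08:00. The difference is 1 h, so the figure is reproduced.

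**Step 2, one clock.** Set the R dose at 0 h and use the 16-day minimum. The T dose is at 384 h, first fluconazole at 384 - 97 = 287 h, the Day -1 laboratory sample at 384 - 25 = 359 h, and the T pre-dose measurements at 384 - 2 = 382 h.

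**Step 3, apply the carry-back literally.** Each scheduled point collects unscheduled values until the next scheduled point. The points whose collection interval crosses a dose are:

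| Data | Receiving point | Interval collected | Hours by phase |
|---|---|---|---|
| Laboratory | R -2:00 | R dose to 24 h | 24 BI 425809 |
| Laboratory | R 215:00 | 215 to 359 h | 49 BI 425809, 23 follow-up, 72 fluconazole |
| Laboratory | T -2:00 | T -2 to T 24 h | 2 fluconazole, 24 BI + fluconazole |
| Vital signs | R -2:00 | R dose to 382 h | 264 BI 425809, 23 follow-up, 95 fluconazole |
| Vital signs | T -2:00 | T -2 to T 3 h | 2 fluconazole, 3 BI + fluconazole |

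Checks: 49 + 23 + 72 = 144 = 359 - 215, and 264 + 23 + 95 = 382.

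**Step 4, dependence on the washout.** The 72 h (97 - 25) and 95 h (97 - 2) under fluconazole do not change with the interval between doses. Only the follow-up part grows: 23 h at 16 days, 47 h at 17, 71 h at 18 and 143 h at 21. Intervals above 16 days are assumptions.

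**Step 5, apply SAP 6.1 instead.** The BI 425809-alone phase closes at 264 h and fluconazole starts no earlier than 287 h, 23 h later. By time taken, no run-in value can count as on-treatment BI 425809 alone. For the same value, SAP 7.8.2 points to R 215:00 and SAP 6.1 to the fluconazole phase.

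**Step 6, the one pre-planned extra sample.** Protocol 3.3.4.1 foresees a next-day ALT/AST control. After the T -25:00 sample it coincides with the scheduled Day 1 sample, and after a -2:00 sample with the scheduled 24:00 sample. After the other treatment-period samples it stays in the same phase. It causes no crossing, so only ad hoc measurements in the windows of step 3 can.

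**The case against.** The strongest reply is that SAP 6.1 and 6.7 already do the work. They are general definitions, they go by actual time, and they would keep fluconazole run-in values out of the BI 425809 on-treatment phase and after-dose values out of baseline. SAP 6.1 also refers the technical detail to an ADS Plan, which is not among the documents and may confine the carry-back to one phase. Nor is the signal lost: individual values are listed, out-of-range and possibly clinically significant laboratory values are marked, and relevant findings become adverse events assigned by onset, with a separate fluconazole phase.

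Most of this stands. A reader might infer that the SAP in fact reports on-drug values as baseline, or fluconazole values as on-treatment BI 425809 alone, for every unscheduled measurement. The documents do not support that. SAP 6.7 protects baseline, SAP 6.1 works against the misattribution, and ECGs and untimed unscheduled vital signs are outside the rule.

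It does not dispose of the point. SAP 7.8.2 and 7.8.3 are the sections that say how by-time-point statistics are built, and they give no boundary. If SAP 6.1 governs phase, an after-dose value can still sit in a pre-dose row without being baseline. Protocol 7.3.4, which goes by planned time, pulls the other way. Two programmers could produce different tables from the same text.

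The vital-sign windows also deserve caution. They rest on a table with damaged columns, and a shifted mark would change them. The laboratory windows are firmer.

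**Conclusion.** The carry-back rule is stated without a stop at dosing, this schedule contains real crossings, and the result conflicts with SAP 6.1. It should be corrected, but the reach is limited: descriptive laboratory and vital-sign summaries by time point. Baseline, individual listings, adverse-event attribution and the primary and secondary PK analyses are untouched.

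The hours in the working are lengths of exposure to the rule, not effect sizes. Nothing in the documents says how many ad hoc measurements to expect in those windows, and with none there is no effect. With one, the value concerns 1 of 15 subjects (6.7%) in its row and could set that row's extreme.

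The conclusion assumes a literal reading of SAP 7.8.2 and 7.8.3, the Flow Chart as extracted, and no overriding rule in the ADS Plan.

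**What to change.** In SAP 7.8.2 and 7.8.3, state two things:

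- The analysis phase of an unscheduled value is set by its actual time, using Table 6.1: 1.
- The value is assigned to the previous scheduled time point only if that point lies in the same phase, and never back across a BI 425809 dose or the first fluconazole dose. Where no such point exists, it is shown as unscheduled within its phase.

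Add a line saying that actual time prevails for unscheduled values, so that the SAP and protocol 7.3.4 no longer point in different directions.

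The worst-value convention for laboratory data and the last-value convention for vital signs can stay; the boundary problem does not require replacing them. The cost is about a sentence or two per section, a small change to the derivation, and possibly an extra unscheduled row in some tables.
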